### 3.8.2 Secondary Analyses of the Primary Efficacy Endpoint

Several secondary analyses will be investigated to assess sensitivity of our estimates of treatment effect to alternative modeling assumptions.

- Active vs. placebo: A secondary estimand of the efficacy of ezogabine will compare both 600 mg/day and 900 mg/day treatment arms vs. placebo, tested at alpha = 0.05. The following SAS code specifies the linear contrast for this comparison:

```
estimate "2|ActvsPlb|dAvg 6&8"
  post*ttrrnd*visit 2 2 0 -2 -2 0 -1 -1 0 1 1 0 -1 -1 0 1 1 0 / cl divisor=4;
```

- Random-slopes model: The visit-specific fixed effects will be replaced with a continuous predictor of month since treatment initiation. Data from Final Safety and Early Termination visits will be placed at their observed follow-up time. Only assessments completed through Week 10, the end of planned study drug exposure, will be included. The following SAS code specifies the model and the linear contrasts used to estimate treatment-dependent differences in rate of change per month:

```
proc mixed data=xxx method=reml;
  where visit in ("Screening","Baseline","Week 04","Week 06","Week 08","Week 10");
  class site id ttrrnd;
  model Value = month ttrrnd*month;
  random intercept / subject=site type=vc;
  random intercept month / subject=id(site) type=un;
estimate "2|600vsPbl|Slope/mn" intercept 0 month 0 ttrrnd*month -1 1 0 / cl;
estimate "2|900vsPbl|Slope/mn" intercept 0 month 0 ttrrnd*month -1 0 1 / cl;
estimate "2|ActvsPbl|Slope/mn" intercept 0 month 0 ttrrnd*month -2 1 1 / cl divisor=2;
```

- Shared-baseline mixed model with pMI for missing data: The shared-baseline mixed model with fixed effects for visits described above for the primary analysis will be applied to datasets generated by placebo multiple imputation (Ayele et al. 2014). Fifty imputed datasets will be generated for a given endpoint.
- PP sample: The primary efficacy model and the secondary random-slopes model and active vs. placebo estimand will be applied to the PP sample.
- loRMT sample: The primary efficacy model and the secondary random-slopes model and active vs. placebo estimand will be applied to the loRMT sample.

- AllQual sample: The primary efficacy model and the secondary random-slopes model and active vs. placebo estimand will be applied to the AllQual sample.

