## **8.9 Final Safety Visit & Telephone Call**

ALS subjects who withdraw consent will be asked to come in for a Final Safety Visit and will be asked to have a final Follow-Up Telephone Call no sooner than 28 days after subject's last known dose of study drug.

The Final Safety Visit should be scheduled as soon as possible, but within 14 days of subject withdrawing consent. The following will be performed:

- Review and document concomitant medications and therapies
- Assess and document AEs
- Perform physical examination
- Perform neurological examination, including MMT

- Perform ophthalmologic examination (may be scheduled separately, but within 14 days of the Final Safety Visit)
- Measure vital signs and weight
- Perform 12-lead ECG
- Collect blood samples and urinalysis for safety clinical laboratory assessments
- Administer ALSFRS-R questionnaire
- Administer the American Urological Association (AUA) Symptom Score survey
- Perform SVC
- Perform hand held dynamometry (HHD - APB bilaterally)
- Administer the suicide prevention (C-SSRS) questionnaire
- Perform neurophysiological testing (TMS and NCS) unless the decision to withdraw consent was due to intolerance of neurophysiological testing.
- Check study drug compliance and collect dosing diary
- Review returned Muscle Symptom Diary
- Complete Fasciculation Assessment
- Perform study drug accountability and collect all unused study drug and empty containers
- Complete Blindedness Questionnaire and Exit Survey

The final Follow-Up Telephone Call phone call will take place no sooner than 28 days after the last known dose of study drug. The following procedures will be performed:

- Review and document concomitant medications and therapies
- Assess and document AEs

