## **2.4 Participant Flow and Site Approval**

After providing informed consent, approximately 5 UHC participants will be screened for eligibility at each site, including assessment of neurophysiology by TMS and TTNCS by one or two neurophysiologists. Each UHC participant will have up to 4 additional neurophysiological testing visits over a span of up to 6 weeks.

After completing TMS and TTNCS assessments of the first UHC participant, sites must receive approval from the Coordination Center before continuing enrollment of UHC participants. Approval will be based on review of TMS and TTNCS data by the respective central reading centers. After completing enrollment of approximately 5 UHC participants, sites must receive approval from the Coordination Center before initiating recruitment of ALS participants.

After a site is activated for recruitment of ALS participants and after each ALS patient provides informed consent and is determined eligible, approximately 120 ALS participants will be randomized to receive ezogabine 600 mg/day, ezogabine 900 mg/day, or placebo in a 1:1:1 ratio, stratified by clinical site. The first dose of study drug is administered at the baseline visit. ALS participants are exposed to study drug for 10 weeks, from baseline to a week 10 telephone call. ALS participants complete in-clinic evaluations at weeks 4, 6, 8, and 12 and complete follow-up by telephone at weeks 2, 10, and 14 to assess for TEAEs and update concomitant medication logs. Participants who discontinue study drug should remain on study following the normal schedule of assessments. Patients withdrawing consent are asked to delay withdrawing consent until after they return for a Final Safety Visit approximately 2 weeks after their last dose of study drug and after they complete a final telephone call 4 weeks after their last dose of study drug.

Detailed descriptions of study procedures and timing are specified in the clinical protocol.

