### 3.8 Efficacy Analysis

#### 3.8.1 Primary Analysis of the Primary Efficacy Endpoint

The primary efficacy analysis will be performed on SICI of the APB after log-transformation in the mITT sample of ALS participants and will use a shared-baseline mixed model with fixed effects for visit (6 levels: Screening, Baseline, and Weeks 4, 6, 8, and 12), treatment group (3 levels: placebo and 600 and 900 mg/day ezogabine) x post-baseline visit (4 levels) and random site-specific intercepts and random participant-specific intercepts and slopes with unstructured covariance. The interaction between fixed effects for treatment group and visit will be restricted to post-baseline visits by including a numeric indicator variable (0 pre-treatment, 1 post-treatment) in the interaction. Use of a shared baseline reflects the true state of the population sampled prior to randomization and has the advantage of adjusting for any chance differences at baseline in a manner similar to analysis of covariance (Liang and Zeger, 2000) with potentially greater efficiency with more than one follow-up visit and drop-out. Random participant-specific slopes will be estimated per month from treatment initiation with all pre-treatment observations assigned a value of 0 months from treatment initiation. Data from Final Safety or Early Termination visits will be assigned to the next scheduled post-baseline visit. The following SAS code specifies the model:

```
proc mixed data=xxx method=reml;
  class site id trrnd visit;
  model Value = visit post*trrnd*visit;
  random intercept / subject=site type=vc;
  random intercept month / subject=id(site) type=un;
```

Treatment-dependent differences in the change from pre-treatment to the average of the week 6 and 8 visits on SICI will be estimated by a linear contrast and tested using a two-tailed Wald-test at alpha = 0.027. The following SAS code specifies the linear contrasts used to obtain the two co-primary estimands (with the sort order for treatment group being placebo, 600 mg/day ezogabine, and 900 mg/day ezogabine, and the sort order for visit being chronological):

```
estimate "2|600vsPlb|dAvg 6&8"
  post*ttrrnd*visit 1 1 0 -1 1 0 -1 -1 0 1 1 0 0 0 0 0 0 / cl divisor=2;
estimate "2|900vsPlb|dAvg 6&8"
  post*ttrrnd*visit 1 1 0 -1 -1 0 0 0 0 0 0 -1 1 0 1 1 0 / cl divisor=2;
```

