### 3.8.3 Secondary Efficacy Endpoints

The key secondary efficacy endpoint of RMT will be analyzed using the same analysis samples and models as specified for the primary efficacy endpoint in Sections 3.8.1 and 3.8.2. Continuous non-key secondary efficacy endpoints and exploratory efficacy endpoints measuring electrophysiology and clinical progression will all be analyzed using the mITT sample and the primary efficacy analysis described in Section 3.8.1. Variables that are strongly right-skewed (e.g., MEP amplitude, ICF) will be log-transformed prior to analysis, and estimates will be back-transformed for reporting.

The binary indicator of good quality TMS recordings will be analyzed in an equivalent generalized mixed model treating the indicator variable as a Bernoulli random variable with logit link.

Weekly cramping frequency data will be analyzed in similar generalized mixed models treating the number of cramps experienced in a week as a negative binomial random variable with log link and with the log of the number of days at risk for cramps as an offset. Similarly, weekly number of days with fasciculations will be analyzed in similar generalized mixed models treating the number of days with fasciculations in a week as a binomial random variable with logit link. Because diary data are only collected after baseline, fixed effects in the model will include treatment group, post-baseline week, and baseline retrospective report of number of cramps experienced in the prior 30-day interval or the experience of fasciculations in the prior 14-day interval.

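### SAP 3.8.2: the random-slopes code selects by visit label while its text selects by time, so some Final Safety and Early Termination records through Week 10 can be lost

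*SAP*

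**What the plan says.** SAP 3.8.2 lists a random-slopes model among the secondary analyses of the primary endpoint. It replaces the visit effects with continuous months since treatment initiation. Two sentences define its data by time: "Data from Final Safety and Early Termination visits will be placed at their observed follow-up time", and "Only assessments completed through Week 10, the end of planned study drug exposure, will be included".

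The SAS code given as the specification of that model selects records differently: "where visit in ('Screening','Baseline','Week 04','Week 06','Week 08','Week 10" (the list ends there). It has no Final Safety or Early Termination label and no condition on month or day.

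Section 3.8.2 does not say what the visit variable holds for these records. The only labelling rule in the SAP is in 3.8.1, for the primary model: "Data from Final Safety or Early Termination visits will be assigned to the next scheduled post-baseline visit". That model has "fixed effects for visit (6 levels: Screening, Baseline, and Weeks 4, 6, 8, and 12", so it has no Week 10 level.

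Three other statements bear on the point:

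- Week 10 is a telephone contact (SAP 2.4: "complete follow-up by telephone at weeks 2, 10, and 14"), so no TMS is scheduled then.
- Final Safety Visits do produce TMS data. Protocol 8.9 lists "Perform neurophysiological testing (TMS and NCS) unless the decision to withdraw consent was due to intolerance of neurophysiological testing".
- The model is also run for the key secondary endpoint (SAP 3.8.3: "The key secondary efficacy endpoint of RMT will be analyzed using the same analysis samples and models as specified").

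**The concern.** Text and code in the same section describe two different data sets, and the code is presented as the definition of the model. Which records enter then depends on a label that the section leaves undefined and a programmer would have to choose.

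The records at risk come from people who leave the study, so any loss is tied to dropout. Protocol 13.5 itself foresees that missingness may be higher in the active arms. An analysis written to use early-withdrawal data at its true time should not lose part of that data through a filter.

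**Working it through.** The plan states no figure here, so there is nothing to reproduce. The check compares text with code and then bounds the size.

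**1. Apply the filter to each possible day.** Take a Final Safety or Early Termination assessment on each of Days 1-70. By the text, all 70 days qualify. Target days are 7 times the week number: Weeks 4, 6, 8, 10 and 12 fall on Days 28, 42, 56, 70 and 84.

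| Content of the visit variable | Days dropped by the code |
|---|---|
| Own Final Safety/Early Termination label | 70 of 70 |
| 3.8.1 rule: next of Weeks 4, 6, 8, 12 | 14 of 70 (Days 57-70, labelled Week 12) |
| Next contact, counting telephone calls | 14 of 70 (Days 1-14, labelled Week 2) |
| Next of Weeks 4, 6, 8, 10, 12 | 0 of 70 |

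No coding keeps a record after Day 70. Only the second row follows a rule written in the SAP. Records kept under it still enter at their true time, because month is continuous. Selection by observed time would keep all 70 days under every coding.

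**2. Which runs are exposed.** SAP 3.5 removes from the PP sample observations made after premature permanent discontinuation of drug. The loRMT and AllQual samples are drawn from PP. SAP 2.4 places the Final Safety Visit about two weeks after the last dose, so most such records are already outside those three samples. That leaves the mITT run, for SICI and RMT. SAP 3.8.3 assigns the other continuous endpoints to the primary model only.

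**3. A ceiling on the size.** The documents give no number or timing of these visits. Assume:

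- loss of 25%, the upper allowance in SAP 3.4, with 10% as an alternative;
- withdrawals even over Days 1-70;
- a Final Safety Visit 0-14 days after withdrawal (Protocol 5.7 allows 14 days);
- usable TMS from every withdrawer.

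Own labels, where every record by Day 70 is dropped:

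- Lag of exactly 14 days: withdrawals on Days 1-56 count, so 56/70 × 25% = 20%.
- Lag uniform on 0-14 days (mean 7): 63/70 × 25% = 22.5%.

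3.8.1 labels, where records on Days 57-70 are dropped: 14/70 × 25% = 5%.

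At 10% loss the same fractions give 8%, 9% and 2%. With 40 per arm, 25% loss means 8 to 9 participants under own labels (0.20 × 40 and 0.225 × 40) and 2 under 3.8.1 labels (0.05 × 40).

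**The case against.** The best defence is that the SAP does have a labelling rule. Under 3.8.1, records through Day 56 pass the filter and enter at their observed time. The list also contains Week 10, a contact without scheduled TMS. A sensible explanation is that this label was meant to catch relabelled late records, in which case nothing is lost. This is plausible, and it means that loss is not certain. But no section states that coding, and 3.8.1 specifies six visit levels without Week 10. If the same variable fed both models, the primary model would gain a seventh level. As written, the stated rule still drops Days 57-70.

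It is also fair that this is one sensitivity model among several, outside the tests governed by the multiplicity section (SAP 3.8.5).

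Three stronger readings are tempting, and the documents do not support them:

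- **The code drops all these assessments.** That needs them to keep their own label, which the SAP does not say.
- **All four samples are affected.** SAP 3.5 already excludes most of these records from PP, loRMT and AllQual.
- **People who leave before Week 6 lose their only post-dose TMS, so the model becomes an analysis of those who stayed.** This arises essentially only with own labels. Under 3.8.1 labels a dropped record on Day 57 or later, with a lag of at most 14 days, implies withdrawal on Day 43 or later (57 − 14), after the Week 6 target of Day 42. Participants enrolled before protocol version 4 also had TMS scheduled at Week 4.

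The percentages are not estimates of what will happen. Death and true loss to follow-up give no visit. Those who only stop drug are asked to stay on the normal schedule. Final Safety TMS is omitted when the testing itself was not tolerated, and poor-quality TMS is excluded.

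**Conclusion.** The point holds as a contradiction between text and code within SAP 3.8.2. Under the SAP's only stated labelling rule, the code drops Final Safety and Early Termination records from Days 57-70 that the text includes. With own labels it drops all of them. With an unstated Week 10 relabelling it drops none.

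The consequence is limited to the mITT run of a secondary model for SICI and RMT. The number of participants cannot be computed from the documents, and the shares worked out above are upper bounds that rest on the listed assumptions. The correction is worth making because it is cheap and because a pre-specified analysis should not turn on an undefined label.

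**What to change.** Replace the label filter with one on actual assessment time: all pre-treatment records, plus every post-dose record, including Final Safety and Early Termination, through Week 10. In outline: `where post=0 or day<=70;` with `day` counted from treatment initiation.

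State the cut-off. The text says only that assessments run through Week 10, which could mean Day 70 or the end of the ±3-day window, Day 73 (70 + 3). Either keeps in-window Week 8 visits (latest Day 59) and excludes in-window Week 12 visits (earliest Day 81), so the choice affects few records, but it should be written down.

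Compute month from the actual date, and add that the visit relabelling in 3.8.1 does not apply to this model.

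The cost is one line of SAS and a short addition to the SAP. No new data are needed, and the primary analysis does not change.

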### 3.8.3 Secondary Efficacy Endpoints

The key secondary efficacy endpoint of RMT will be analyzed using the same analysis samples and models as specified for the primary efficacy endpoint in Sections 3.8.1 and 3.8.2. Continuous non-key secondary efficacy endpoints and exploratory efficacy endpoints measuring electrophysiology and clinical progression will all be analyzed using the mITT sample and the primary efficacy analysis described in Section 3.8.1. Variables that are strongly right-skewed (e.g., MEP amplitude, ICF) will be log-transformed prior to analysis, and estimates will be back-transformed for reporting.

The binary indicator of good quality TMS recordings will be analyzed in an equivalent generalized mixed model treating the indicator variable as a Bernoulli random variable with logit link.

Weekly cramping frequency data will be analyzed in similar generalized mixed models treating the number of cramps experienced in a week as a negative binomial random variable with log link and with the log of the number of days at risk for cramps as an offset. Similarly, weekly number of days with fasciculations will be analyzed in similar generalized mixed models treating the number of days with fasciculations in a week as a binomial random variable with logit link. Because diary data are only collected after baseline, fixed effects in the model will include treatment group, post-baseline week, and baseline retrospective report of number of cramps experienced in the prior 30-day interval or the experience of fasciculations in the prior 14-day interval.

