## 3.2 Study Endpoints

### 3.2.1 Efficacy Endpoints

The primary efficacy endpoint is the change from pre-treatment to the average of the week 6 and week 8 visits in paired-pulse short-interval intracortical inhibition (SICI) assessed by TMS.

The key secondary efficacy endpoint is the change from pre-treatment to the average of the week 6 and week 8 visits in resting motor evoked potential (MEP) threshold (RMT) assessed by TMS.

The other secondary efficacy endpoints are the change from pre-treatment to the average of the week 6 and week 8 visits in the following measures.

TMS measures:

- MEP amplitude at 120% of RMT,
- Intracortical facilitation (ICF), and
- Cortical silent period (CSP).

TTNCS measures:

- Strength duration time-constant (SDTC),
- Depolarizing and hyperpolarizing electrotonus at 90 to 100 ms (TEd(90-100 ms) and TEh(90-100 ms)),
- Recovery cycle measures of relative refractory period (RRP), superexcitability, and subexcitability, and
- Compound motor action potential (CMAP).

Clinical measures:

- ALS Functional Rating Scale-Revised (ALSFRS-R) total score,
- Slow vital capacity (SVC),
- Abductor pollicis brevis (APB) muscle strength by hand-held dynamometry (HHD),
- Muscle cramping frequency and pain, and
- Fasciculation occurrence and interference with daily life.

Exploratory efficacy measures include: maximum amplitude, minimum amplitude, midpoint of activation, and slope at the midpoint of activation from input/output curves; rheobase, TEd(40-60 ms), TEh(10-20 ms), TEd(peak), subexcitability after second pre-pulse, and stimulus for 50% maximum response assessed by TTNCS; MEP amplitude at 120% of RMT divided by CMAP.

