### **3.3.7 Fasciculations**

Data on muscle fasciculations are captured at baseline and each post-baseline clinic visit by retrospective report of the prior 14-day interval. Data are captured on the experience of any fasciculations, the average duration of fasciculations, the association of fasciculations with exertion or times of rest, the degree to which fasciculations interfere with daily activities, and interference of fasciculations with sleep. Prospective data on fasciculations are recorded starting at baseline by participants in daily diaries and then summarized as weekly summaries indicating the number of days with no fasciculations, with fasciculations after exertion that did not substantially interfere with daily activities, with fasciculations at rest or after exertion that did

not substantially interfere with daily activities, and fasciculations that substantially interfered with daily activities.

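### The only fasciculation model counts any-versus-none days, so milder fasciculations cannot change its result; a graded model should be added beside it

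*SAP*

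**What the plan says.** SAP 3.2.1 lists among the secondary efficacy endpoints "Fasciculation occurrence and interference with daily life". The protocol's summary of objectives and endpoints, and its section 10.2.7, both say that the diary captures severity of fasciculations, daily in the latter.

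SAP 3.3.7 reduces the daily diary to weekly counts of days in four categories. The first two are "the number of days with no fasciculations, with fasciculations after exertion that did not substantially interfere with daily activities". The third is days "with fasciculations at rest or after exertion that did" not substantially interfere. The fourth is "fasciculations that substantially interfered with daily activities". The same section describes a clinic-visit form with 14-day recall, which also records "the degree to which fasciculations interfere with daily activities, and interference of fasciculations with sleep".

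SAP 3.8.3 gives one model for fasciculations, "treating the number of days with fasciculations in a week as a binomial random variable with logit link". Its fixed effects are treatment group, post-baseline week and, at baseline, "the experience of fasciculations in the prior 14-day interval". The general mixed-model rule in that section is for continuous measures of electrophysiology and clinical progression, so it does not reach a categorical rating. SAP 3.6 uses fasciculation intensity and interference only to describe the samples at baseline. Protocol 13.4 gives no fasciculation model.

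**The concern.** The model keeps one of the three boundaries between the four categories, that between none and any. The endpoint in SAP 3.2.1 has two parts, and the second, interference, has no planned test.

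A drug meant to lower motor neuron excitability might well make fasciculations less intrusive without clearing whole days of them. A participant who goes from substantial interference on all seven days to exertion-only fasciculations on all seven days scores 7/7 both times. At stake is the trial's ability to test a real effect of this kind on a secondary endpoint, using grades that participants record every day.

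**Working it through.** **1. The plan's own power figure.** The only one is for SICI (SAP 3.4). With a difference of 25, SD 30, two-sided alpha 0.027 and a two-sample t-test, 80% power needs 29 evaluable per arm, and 29/0.75 = 38.7, so 39 against the stated 40. With 40 × 0.75 = 30 evaluable, power is 82.8%. The figure reproduces but does not concern fasciculations. Only the 30 per arm is carried forward. Every other input below is an assumption, because the documents give no distribution over the four categories.

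**2. Effect on severity only.** The analysed count is diary days minus days with none. If treatment changes only how non-zero days divide among the upper three categories, the distribution of that count is the same in every arm, so power equals alpha. Two simulations agree:

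- 70 diary days (10 weeks × 7), severity-only odds ratio 3: any/none about 3–7%, ordinal model 27–67%.
- 28 diary days, participant random-intercept SD 2.0, two-sided 5%, 1,500 runs, t-tests on each participant's share of any-fasciculation days versus mean 0–3 score: any/none 4–6%. The four-level score at odds ratios 0.3 and 0.15 had 19% and 37% (category shares 50/20/20/10), 35% and 64% (20/30/30/20), and 50% and 86% (5/30/40/25).

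**3. Same shift at every boundary.** Inputs: 30 per arm, random-intercept SD 1.5, cumulative log odds ratio 1.1 (odds ratio 3), two-sided 5%. Shares (none to substantial interference) are 5/20/45/30, 10/20/45/25, 20/20/40/20 and 40/20/30/10. Power in percent, ordinal versus any/none:

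| Diary days | 5% none | 10% none | 20% none | 40% none |
|---|---|---|---|---|
| 14 (size-adjusted) | 75 vs 49 | 73 vs 62 | 77 vs 69 | 79 vs 73 |
| 42 | 79 vs 67 | – | – | – |
| 70, first set | 79 vs 70 | 79 vs 76 | – | 80 vs 80 |
| 70, second set | 81 vs 73 | – | 79 vs 77 | 75 vs 74 |

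Over 70 days the gap is 79 − 70 = 9 points at most and 80 − 80 = 0 at least. The first 70-day set used 400 runs, so each figure has a standard error of about √(0.75 × 0.25/400) = 2.2 points, and gaps of 1 to 3 points are indistinguishable from none.

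**4. Why the gap shrinks with more days.** For a single day, the share of information kept by the any/none cut under proportional odds is 3p(1−p)/(1−Σpₖ³), with p the share of none days. At 5% none this is 3 × 0.05 × 0.95/(1 − 0.12625) = 0.1425/0.87375 = 16%. For the other three distributions it is 31%, 53% and 80%. Those ratios ignore variation between participants. Over 70 days each participant's own level is estimated well from either scale, between-participant variance dominates, and the two analyses draw together.

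**5. Effect at the none/any boundary only.** In the 28-day simulation with odds ratio 0.15, any/none against the four-level score gave 69% vs 19% (50% none), 91% vs 22% (20% none) and 80% vs 12% (5% none). With 50% none and a common shift (odds ratio 0.3) it gave 57% vs 54%.

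**The case against.** The case for the planned model is substantial. Counting days with fasciculations is a clear summary, and it is the better test if the drug clears mild days (step 5). SAP 3.3.7 never calls the four categories ordered. They mix trigger with interference, and the second and third overlap, since both include fasciculations after exertion. Protocol 10.2.7.2 says that what counts as interference may differ between subjects. A participant random intercept absorbs a uniform difference in how people grade, but not differently spaced thresholds, so proportional odds is open to doubt. These points stand. They argue against replacing the planned model, not against adding to it.

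A reader might infer several stronger things:

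- *A general power loss of 6 to 25 points.* That range belongs to the 14-day row. SAP 3.2.1 does frame the other secondary endpoints around weeks 6 and 8, but the diary model in SAP 3.8.3 has post-baseline week as a fixed effect and names no two-week contrast, so all weeks contribute.
- *Milder fasciculations cannot be seen at all.* They cannot move the planned test. The four weekly counts and the visit-form interference item are still collected, and SAP 3.1.2 plans counts and percentages for categorical outcomes.
- *Only complete abolition is detected.* Fewer fasciculation days per week is exactly what the binomial model detects.
- *The baseline covariate is yes/no and near its ceiling.* The wording suggests a yes/no item, but the coding is not stated and no baseline distribution is given.

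**Conclusion.** The point holds in a limited form. The planned fasciculation test has power equal to alpha against any effect confined to the non-zero grades, by construction and whatever the distribution. The gain from a graded model against such an effect depends on assumptions: 27–67% power over 70 days, or 19–86% over the 28-day scenarios.

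For an effect that shifts all grades alike, the cost of the cut over the ten treatment weeks is about 0 to 9 points. It is larger only if few diary days are used and nearly every day has fasciculations. The 70-day figures assume a constant effect, although SAP 2.6 has titration at the start and a taper in weeks 9 and 10. They also rest on one between-participant SD and one odds ratio.

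The documents do not support saying that the any/none model is wrong or generally weaker. This is a non-key secondary endpoint reported with nominal p-values (SAP 3.8.5), so the primary and key secondary conclusions do not depend on it.

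**What to change.** In SAP 3.8.3, keep the any/none binomial model as planned. Beside it, pre-specify a cumulative-logit mixed model of the days in each of the four SAP 3.3.7 categories per week, with the same fixed and random effects, except that its baseline covariate is the degree of interference already collected on the Baseline Visit form. State the assumed order of the categories. If that order or proportional odds is judged doubtful, use instead a binomial mixed model of days with substantial interference, which needs neither and matches the wording of the endpoint.

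The change is to SAP text and one extra model, with no new data, and should be made before unblinding. It costs one more nominal p-value on a non-key secondary endpoint and, for the cumulative-logit version, a proportional-odds assumption.
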